### Expected Adverse Events in Children with Sickle Cell Disease

- Acute chest syndrome
- Aplastic crisis
- Anemia
- Bacteremia
- Cholelithiasis, cholecystitis, biliary tract obstruction
- Dehydration
- Fever
- Gastroenteritis
- Headache
- Hematuria
- Hyposthenuira
- Hyperbilirubinemia
- Leukocytosis
- Nocturia
- Obstructive sleep apnea
- Osteomeylitis
- Otitis media
- Pain
- Pharyngitis
- Pneumonia
- Priapism
- Splenic sequestration
- Upper respiratory tract infections
- Urinary tract infections
- Tachycardia

Tachypnea  
Thrombocytosis

#### Serious adverse event (SAE)

Results in death  
Life-threatening (participant at risk of death at the time of the event)  
Requires or prolongs hospitalization (unless an expected event).  
Causes persistent or significant disability.  
Results in a congenital anomaly.  
Other medical events (in the opinion of the investigator) that may put the participant at risk or require intervention to prevent a serious AE.

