### Reporting of Events

Serious safety events will be reported to the DSMB and IRB which will make recommendations to the study PI. Unexpected SAE will be reported to the DSMB and IRB within 7 calendar days if fatal or life-threatening, and within 15 calendar days if not. All SAE will be provided to the DSMB quarterly. All AE (serious and non-serious) will be reported to the DSMB every six months.

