#### Potential Risks

Losartan: This medication is FDA approved to treat hypertension. The FDA warnings include fetal toxicity (Pregnancy Category D) and Hypotension-Volume Depleted Patients. Female participants will have monthly pregnancy tests performed and educated to stop Losartan immediately if pregnant. Participants will be excluded if they are on a medication that leads to volume depletion (diuretics) and educated about volume depletion. Precautions for losartan include 1)hypersensitivity (Angioedema)- participants will be educated on angioedema and immediately removed for life threatening events, 2) impaired hepatic function- participants will have monthly liver function tests, 3) impaired renal function in patients whose renal function depends on the renin-angiotensin-aldosterone system (i.e. CHF), 4) electrolyte imbalance- participants will have monthly electrolyte levels.

Alternative treatments: The alternative to participation in this trial is to have usual care, with an anti-hypertensive medication.

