## Data Safety and Monitoring Board

We will identify investigators (at least 4 members to include a pediatric hypertension expert, sickle cell expert, patient representative, and biostatistician) to participate in an independent DSMB to monitor study safety and minimize research associated risk. Incidence of adverse events during the 6 month period will be analyzed during all mentoring meetings and independently by the DSMB. The percentage and 95% confidence intervals for serious adverse events and adverse events will be recorded and sent to DSMB every 3 months. The DSMB will evaluate excessive SAEs overall or in any one group and consider either: 1) reducing the dose of losartan or 2) closing the study and offering an alternative hypertensive medication. Patients will be withdrawn from the trial if they experience angioedema, recurrent symptomatic hypotension despite dose reduction, hyperkalemia, or recurrent symptomatic hypoglycemia.

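### The SAE definition exempts hospitalization for expected events, including dehydration and gastroenteritis, with no exception when losartan may have contributed, so the by-arm SAE review can undercount such admissions

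*Combined protocol and SAP*

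**What the plan says.** Section 7, Serious adverse event (SAE), lists hospitalization as a criterion in these words: "Requires or prolongs hospitalization (unless an expected event". The last criterion on the same list is discretionary: "Other medical events (in the opinion of the investigator) that may put the participant at risk", or that require intervention to prevent a serious AE.

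The list directly above is headed "Expected Adverse Events in Children with Sickle Cell Disease". It has 27 entries, among them dehydration and gastroenteritis alongside pain, fever and upper respiratory infection.

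Potential Risks says of losartan: "The FDA warnings include fetal toxicity (Pregnancy Category D) and Hypotension-Volume Depleted Patients". It then adds: "Participants will be excluded if they are on a medication that leads to volume depletion (diuretics) and educated about volume depletion".

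On monitoring, the Data Safety and Monitoring Board section says "The DSMB will evaluate excessive SAEs overall or in any one group", and gives dose reduction or study closure as the options. It also says: "The percentage and 95% confidence intervals for serious adverse events and adverse events will be recorded and sent to DSMB every 3 months". Under Reporting of Events, expectedness governs expedited reports: "Unexpected SAE will be reported to the DSMB and IRB within 7 calendar days if fatal or life-threatening", and within 15 days otherwise. All SAEs go to the DSMB quarterly and all AEs every six months.

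Section 1.1.b makes the safety of the two dosing strategies Secondary Objective 2. Section 9.2 has no separate safety objective. Under its Objective 1 it leaves evaluation of losartan's safety during the trial to the DSMB.

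**The concern.** Expectedness is used twice. In Reporting of Events it decides how fast an SAE is reported, which is its usual job. In the SAE definition it also decides whether a hospitalization is serious at all. The list describes background sickle cell disease, but two of its terms describe the setting in which the protocol says losartan can do harm. A participant on losartan admitted with dehydration is outside the hospitalization criterion, and the text does not ask whether the drug may have contributed.

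This matters because the DSMB's two named actions are tied to excess SAEs overall or in one group. The arms differ in how far blood pressure is lowered: below the 75th percentile against below the 95th. If admissions recorded only as dehydration or gastroenteritis differed between arms, the SAE comparison need not show it. The route back into the SAE count is investigator opinion. Section 6.3 has the PI and coordinator titrate to each arm's target, so they know the arm, and the coordinator also records the AEs.

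**Working it through.** **1. Which admissions are affected.** The one inferred step is that an expected event in the SAE definition means an entry on the list directly above it. The heading and position make that the natural reading.

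| Admission recorded as | On the expected list? | SAE by the hospitalization criterion? |
|---|---|---|
| Dehydration | Yes | No |
| Gastroenteritis | Yes | No |
| Pain, fever | Yes | No |
| Hypotension, syncope | No | Yes |
| Kidney injury, hyperkalemia | No | Yes |

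The same clinical episode (volume loss with low blood pressure) can fall either side of the line, depending on the term recorded.

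**2. The plan's own figures.** Section 9.1: 0.30 × 200 = 60 eligible, 40 enrolled, and 40 × (1 − 0.10) = 36 retained, above the stated 30. These reproduce. With equal allocation (assumed), 40 / 2 = 20 per arm. The plan states no SAE rate, admission rate or numeric DSMB trigger, so there is no figure on this point to check.

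**3. Illustration at 20 per arm.** The counts are assumed. Suppose x participants in an arm have an exempt admission, none is upgraded and there is no other SAE. The SAE table shows 0/20, with exact 95% upper limit 1 − 0.025^(1/20) = 16.8%. If the admissions counted (exact Clopper-Pearson intervals):

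| x | SAE table now | If counted |
|---|---|---|
| 1 | 0% (0 to 16.8%) | 5% (0.1 to 24.9%) |
| 3 | 0% (0 to 16.8%) | 15% (3.2 to 37.9%) |
| 5 | 0% (0 to 16.8%) | 25% (8.7 to 49.1%) |

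**4. Chance that the rule has any effect in an arm.** This is 1 − (1 − p)^20 for an assumed six-month admission probability p. It is 64% at p = 5%, 88% at 10% and 99% at 20%.

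**5. How much of a true excess would remain visible.** Assume 5% in the standard arm, 10% to 30% in the intensive arm, and a share q of these admissions entering the SAE count by another route. The excess left is (p − 0.05) × q:

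- q = 0: 0 points
- q = 0.25: 1.25 to 6.25 points
- q = 0.50: 2.5 to 12.5 points
- q = 1: 5 to 25 points, nothing lost

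The documents do not fix p or q, so the result runs from no loss to complete loss.

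**6. Unequal upgrading.** If both arms truly had 20% and investigators upgraded 50% in one arm and 20% in the other, the expected SAE participants would be 20 × 0.20 × 0.50 = 2.0 against 20 × 0.20 × 0.20 = 0.8. That would be a difference with no cause in the drug.

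**The case against.** The strongest reply is that the warning concerns hypotension, and hypotension is not on the expected list. Neither are syncope, kidney injury or hyperkalemia, so admissions recorded as any of these remain SAEs. That stands, and it confines the point to admissions recorded only under a listed term.

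A reader might infer that exempt admissions are invisible to the DSMB. The documents do not support this. They remain CTCAE-graded AEs, AE percentages go to the DSMB every 3 months, and all AEs go every six months. Nor does any section say that the AE report is a single pooled percentage; it could be a listing by event. What remains is that no section asks for admissions by arm and term. The exemption also moves these admissions out of the quarterly SAE report, when each participant is followed for six months. Symptom questions at each visit, monthly metabolic profiles and the withdrawal rule for recurrent symptomatic hypotension protect individuals, but they are not a comparison of arms.

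A reader might also infer that the intensive arm will have more dehydration admissions. The protocol says volume depletion makes hypotension on losartan a hazard. It does not say that losartan or a lower target causes dehydration.

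Finally, full counting would not give this trial a powered safety comparison. At 4/20 against 1/20 the difference is 15 points with a Newcombe 95% interval of −7 to 37. That is fair. The purpose is to make a signal visible to the DSMB, not to test it.

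**Conclusion.** The point holds in a limited form. As written, the hospitalization criterion leaves out admissions recorded only as dehydration or gastroenteritis, even when losartan may have contributed, and these can be missing from the SAE count on which the DSMB's stated actions rest. The investigator-opinion and life-threatening criteria and the AE reports narrow the gap without closing it. The first is discretionary and exercised by staff who know the arm, the second covers only the most severe cases, and the third is not what the DSMB's excess-event rule names.

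The size cannot be estimated from the documents. Every rate, recovery share and count in the illustrations is an assumption, apart from 20 per arm, which follows from the planned 40 with equal allocation. The conclusion rests on the wording, together with the reading that expected events are those on the adjacent list.

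A reader might conclude that the whole exemption must go. That does not follow. If 30% to 60% of participants had some other admission in six months (assumed), that would be 12 to 24 of 40. With background admissions independent of dehydration and equal in both arms, a 15-point dehydration excess would appear in an all-cause figure as (1 − 0.30) × 15 = 10.5 to (1 − 0.60) × 15 = 6.0 points. Exempting routine sickle cell admissions is a defensible way to limit that noise.

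**What to change.** Two changes in Section 7.

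- **SAE definition.** Keep the exemption for background sickle cell admissions such as pain and fever. State that it does not apply to an admission for dehydration or gastroenteritis, or to any admission to which losartan may have contributed. The first part works by term and needs no judgement. The second is a backstop for other listed events.
- **DSMB report.** In the 3-monthly report, give all hospitalizations by arm and by term, exempt or not, with counts and 95% confidence intervals. Dehydration or volume depletion, hypotension or syncope, kidney injury and hyperkalemia should each have a separate line. This table does not depend on how an admission was classified or on a causality opinion from someone who knows the arm.

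Reporting of Events can stay as it is, with expectedness deciding only which SAEs need 7- or 15-day reports. The changes need no new visits or tests. The cost is a few more SAE forms and one extra table per DSMB report.

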#### Potential Risks

Losartan: This medication is FDA approved to treat hypertension. The FDA warnings include fetal toxicity (Pregnancy Category D) and Hypotension-Volume Depleted Patients. Female participants will have monthly pregnancy tests performed and educated to stop Losartan immediately if pregnant. Participants will be excluded if they are on a medication that leads to volume depletion (diuretics) and educated about volume depletion. Precautions for losartan include 1)hypersensitivity (Angioedema)- participants will be educated on angioedema and immediately removed for life threatening events, 2) impaired hepatic function- participants will have monthly liver function tests, 3) impaired renal function in patients whose renal function depends on the renin-angiotensin-aldosterone system (i.e. CHF), 4) electrolyte imbalance- participants will have monthly electrolyte levels.

Alternative treatments: The alternative to participation in this trial is to have usual care, with an anti-hypertensive medication.

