## 2.2.c. Exclusion Criteria for Feasibility Trial Screening

1. Participant with history of angioedema to prior ARB or ACE inhibitor
2. Participants with moderate to severe renal impairment (GFR <60mL/min/1.73m^2)
3. Co-administration of another hypertensive medication
4. History of known bilateral renal artery stenosis, unilateral renal artery stenosis to a solitary kidney
5. Hyperkalemia at time of screening (K>6 mmol/L- non-hemolyzed sample)
6. Pregnancy
7. Current use of lithium, digitalis, warfarin

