## 7. Safety Reporting and Adverse Events

All patients will have standard of care monthly clinic visits while on losartan. Side effects and adverse events will be recorded by study coordinator at each clinic visit. Participants will have monthly complete metabolic profiles for monitoring of potassium, liver function tests. Participants will be asked about symptoms of hypotension.

**Hyperkalemia:** Participants will have potassium monitored monthly. Potassium > 6 mEq/L will be repeated and if abnormal, the dose of losartan will be decreased. If participants are still >95th percentile blood pressure when hyperkalemia, a diuretic will be added as standard of care.

**Liver function tests:** Participants baseline AST and ALT will be recorded and compared to monthly AST and ALT levels. If AST/ALT is greater than three times the upper limit of normal, losartan will be stopped

**Symptomatic hypotension:** Participants will be asked about symptoms of hypotension prior to enrollment and at each visit including feeling lightheaded or dizzy. Participants will be asked to call the study PI to notify them of symptoms and take a blood pressure at home.

**Allergic reaction:** Participants will be asked to call the study PI if they develop swelling of the face, lips, throat, and/or tongue. Participants will be asked to describe any new rashes.

**Musculoskeletal:** Participants will be asked to describe any muscle pain, muscle tenderness, or dark urine.

Additional AEs will be documented based on participant interview and voluntary disclosure of additional toxicities. AEs will be scored using the Common Toxicity Criteria for Adverse Events 4.0.

[http://evs.nci.nih.gov/ftp1/CTCAE/CTCAE\\_4.03\\_2010-06-14\\_QuickReference\\_5x7.pdf](http://evs.nci.nih.gov/ftp1/CTCAE/CTCAE_4.03_2010-06-14_QuickReference_5x7.pdf)

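### The diuretic exclusion promised under Potential Risks is missing from the eligibility list, and two sections handle hyperkalemia differently

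*Combined protocol and SAP*

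**What the plan says.** **Diuretics at entry.** Potential Risks (section 7) names the relevant warnings: "The FDA warnings include fetal toxicity (Pregnancy Category D) and Hypotension-Volume Depleted Patients". For volume depletion it offers two protections. One is education; the other is an exclusion: "Participants will be excluded if they are on a medication that leads to volume depletion (diuretics").

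Section 2.2.c, the exclusion list for screening, has seven items. Two concern medication: item 3, "Co-administration of another hypertensive medication", and item 7, "Current use of lithium, digitalis, warfarin".

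**Hyperkalemia during the trial.** Under Hyperkalemia in section 7, a potassium above 6 mEq/L is repeated and, if the repeat is abnormal, losartan is reduced. If blood pressure is still above the 95th percentile, "a diuretic will be added as standard of care". The Data Safety and Monitoring Board section has a different provision: "Patients will be withdrawn from the trial if they experience angioedema, recurrent symptomatic hypotension despite dose reduction, hyperkalemia", with a further event named after it.

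**The concern.** An exclusion put forward as protection against a named drug warning should appear where eligibility is checked. If it appears only in the risk narrative, it depends on the screener remembering a passage many pages away from the list. What is at stake is that a participant whom the protocol says is excluded could be randomized because the list did not prompt the question.

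The hyperkalemia passages raise a second question, about participant status. One describes a participant whose losartan dose is lowered; the other describes a participant who leaves the trial. Site staff could follow either and be in line with the protocol. Section 9.2 treats retention as a result of this feasibility trial, so who counts as withdrawn should not depend on which page was read.

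**Working it through.** No calculation underlies this point, and the plan gives no figure to reproduce. The check is a comparison of the texts.

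**Step 1: is the diuretic exclusion anywhere in the eligibility criteria?** The seven items in 2.2.c cover prior angioedema, reduced GFR, another hypertensive medication, renal artery stenosis, high potassium, pregnancy, and three named drugs. None mentions diuretics or volume depletion. The cohort criteria (2.2.a), the screening inclusion criteria (2.2.b) and the randomization criteria (2.2.d) contain no such condition either.

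**Step 2: does item 3 do the work?** Read literally, a hypertensive medication is one that raises blood pressure, which cannot be the intent. The Data Safety and Monitoring Board section uses the same adjective for the alternative treatment to be offered if the study closes, so antihypertensive is clearly meant. On that reading:

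| Candidate at screening | Potential Risks | Section 2.2.c |
|---|---|---|
| Diuretic taken for blood pressure | Excluded | Excluded by item 3, once read as antihypertensive |
| Diuretic taken for another reason | Excluded | Not clearly covered by any item |

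Potential Risks defines its exclusion by the drug's effect on volume, item 3 by its use against hypertension. The second row is the gap.

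**Step 3: what happens to a participant with hyperkalemia?**

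| Situation | Section 7, Hyperkalemia | Data Safety and Monitoring Board section |
|---|---|---|
| Potassium above 6 mEq/L, not yet repeated | Repeat | Withdrawal for hyperkalemia; no threshold or confirmation stated |
| Repeat abnormal, blood pressure not above 95th percentile | Reduce losartan | Withdrawal |
| Repeat abnormal, blood pressure above 95th percentile | Reduce losartan and add a diuretic | Withdrawal |

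In the withdrawal sentence, persistence after dose reduction is attached to hypotension. Hyperkalemia stands as a separate item with no qualifier. The conflict is present in the second row, so it does not depend on the diuretic.

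**Step 4: scale.** The documents give no rate of diuretic use or of hyperkalemia. As a unit of scale only, with 40 enrolled (section 9.1), classifying one participant as withdrawn rather than retained changes the retention rate by 1/40 = 2.5 percentage points. That says nothing about how often it would happen.

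**The case against.** Several counter-arguments are fair.

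- **The exclusion is in the protocol.** Potential Risks states it in mandatory terms, and nothing says that 2.2.c overrides it. This stands. A reader might infer that the protocol permits diuretic users to enroll; it does not. The fault is that the list fails to repeat the rule, so it can be overlooked.
- **Item 3 covers much of the ground.** Every participant has raised clinic blood pressure (2.2.b), so blood pressure is an obvious reason for a diuretic here, and item 3 catches that case. This narrows the gap to diuretics taken for other reasons, which the documents do not suggest are common. It does not close it.
- **An entry exclusion and a later added diuretic can coexist.** A reader might infer a three-way contradiction between Potential Risks, 2.2.c and the diuretic added under Hyperkalemia. The documents do not support that. The exclusion reads naturally as a condition at entry, while the added diuretic is management of a later laboratory event. Potential Risks sets no time limit, but that makes it ambiguous, not contradictory.
- **The hyperkalemia passages might be sequential.** Withdrawal could be meant only if dose reduction fails, or the diuretic could be meant as care after leaving the trial. Either would reconcile the two passages, but neither is written down.

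A reader might also infer that an added diuretic contaminates the comparison of blood pressure or dipping between arms and calls for its own sensitivity analysis. The documents do not carry that far. The trigger is narrow (a confirmed potassium above 6 mEq/L together with blood pressure above the 95th percentile), its frequency cannot be estimated, and section 2.2 already specifies intention to treat. If the 40 split equally, one participant is 1/20 = 5% of an arm, but this measures neither frequency nor bias.

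**Conclusion.** The point holds as two minor inconsistencies. First, the exclusion of diuretic users stated under Potential Risks is not carried into section 2.2.c, and item 3 reaches at most those taking a diuretic for blood pressure. This is the firmer half, and it stands whether or not the exclusion is limited to entry. Second, section 7 keeps a participant with confirmed hyperkalemia on a lower losartan dose, with a diuretic in some cases, while the Data Safety and Monitoring Board section withdraws for the same event, leaving trial status unclear.

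Sample size and error rates are unaffected, and the number of participants involved cannot be estimated from the documents. The conclusion assumes that item 3 means antihypertensive medication and that the exclusion under Potential Risks is a condition at entry. If the exclusion was meant to run throughout the trial, the added diuretic would need reconciling with it as well. No view is taken on which clinical rule is right.

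**What to change.** 1. Reconcile section 2.2.c with Potential Risks so that both state the same rule on diuretics and other volume-depleting medication, and say whether it applies only at entry.
2. Correct the wording of item 3 in 2.2.c.
3. Reconcile the Hyperkalemia paragraph of section 7 with the withdrawal sentence in the Data Safety and Monitoring Board section, so that it is clear whether and when a participant with hyperkalemia leaves the trial.

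The content of each rule is for the clinical team to decide. The cost is a few sentences across four places, with no change to sample size or to the analysis. Optionally, record the date and arm of any diuretic started during the trial, at the cost of one data field. No additional analysis is requested.
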